5.1.2 Assessment of patient reported outcomes

Patients should complete all study questionnaires in the following order: LupusPRO, SF-36, FACIT-F at the trial site at each time point indicated in the [Flow Charts](#) in a quiet area/room prior to any assessments or treatments and, if possible, before any interactions with the investigator or any member of the study team. The trial site staff /investigator may record the study questionnaires on behalf of the patient only if the patient has difficulty in writing or unable to read. This must be clearly documented in the patient medical notes.

The questionnaires generally take about 5-10 minutes to complete. Refer to the ISF for a copy of the questionnaires. The SF-36 version 2 will be used in this trial.

5.1.3 Assessment of SLEDAI:

The SLEDAI assessment should take approximately 10 minutes to complete. The investigator will complete the SLEDAI assessments (version SELENA-SLEDAI) based on examination of the patient, their medical history including symptoms over the last 10 days and their laboratory results.

Laboratory tests may be considered for use in scoring the SLEDAI if they are drawn -10 to +7 days from the date of assessment and cannot be used to complete more than one assessment.

5.2 ASSESSMENT OF SAFETY

Safety will be assessed descriptively based on:

- Physical examination
- Vital signs
- Safety laboratory tests
- Electrocardiogram
- Adverse events (including drug-related AEs)
- Adverse events of special interest (AESI)
- Serious adverse events

5.2.1 Physical examination

Physical examinations will be performed at the time points specified in the [flow charts](#). Complete physical examination will include general appearance, vital signs assessment and evaluation of organ systems (eyes, ears, nose, mouth, throat, neck and respiratory, cardiovascular, chest, gastrointestinal, lymphatic, musculoskeletal, skin, neurologic and psychiatric). Height (at screening only) and body weight will also be measured.

Targeted physical examination will include weight, vital sign assessment and evaluation of organ systems associated with AE(s) symptoms or laboratory abnormalities.

All abnormal findings at baseline will be recorded on the Medical History/Concomitant Diagnosis eCRF page. New abnormal findings or worsening of baseline conditions detected at the subsequent physical examinations will be recorded as adverse events on the appropriate eCRF page.

5.2.2 Vital signs

Vital signs evaluation includes temperature, pulse rate and systolic/diastolic blood pressure will be performed at the time points specified in the [Flow Charts](#). Pulse rate and blood pressure will be measured after patients have been sitting comfortably for at least five minutes. Measurement of vital signs should precede blood sampling to avoid potential impact on vital measurements.

Any abnormal findings shall be evaluated by the investigator and confirmed whether they qualify to be documented as adverse event.

5.2.3 Safety and immunology laboratory parameters

The safety and immunology laboratory parameters to be assessed are listed in [Table 5.2.3:1](#). Patients do not have to be fasted for the blood sampling. Refer to the flowcharts for blood sampling time points.

Table 5.2.3:1 Safety and immunology laboratory tests

Category	Test name	Frequency
Haematology	Haematocrit Haemoglobin Red Blood Cell Count / Erythrocytes White Blood Cells / Leukocytes Platelet Count / Thrombocytes	At every visit until EOT (inclusive), repeat after EOT only if clinically significant findings at the discretion of investigator.
	Erythrocyte sedimentation rate	Analysed locally at baseline, weeks 12, 26 and 52.
	Reticulocyte Count	At baseline, weeks 12, 26 and 52.
Diff. Automatic	Relative count: Neutrophils, Eosinophils, Basophils, Monocytes, Lymphocytes	At every visit until EOT (inclusive), repeat after EOT only if clinically significant findings at the discretion of investigator.
Diff. Manual	Neutrophils, bands (Stabs) Neutrophils, polymorphonuclear Eosinophils, Basophils, Monocytes, Lymphocytes	Only if Diff. Automatic is abnormal (reflex test).

Table 5.2.3:1 Safety and immunology laboratory tests (Cont.)

Coagulation	Partial Thromboplastin Time Prothrombin time (Quick and INR)	At every visit until EOT (inclusive), repeat after EOT only if clinically significant findings at the discretion of investigator.
	Fibrinogen	At baseline, weeks 12, 26 and 52. Repeat after EOT only if clinically significant findings.
Enzymes	AST(GOT), ALT(GPT) Alkaline Phosphatase Creatine Kinase (CK) CK-MB (only if CK is elevated) Gamma-Glutamyl Transferase Lactate Dehydrogenase	At every visit until EOT (inclusive), repeat after EOT only if clinically significant findings at the discretion of investigator.
	Lipase, Amylase	At baseline, weeks 12, 26 and 52.
Electrolytes	Calcium, Sodium, Potassium, Chloride	At every visit until EOT (inclusive), repeat after EOT only if clinical significant findings at the discretion of investigator.
Substrates	Plasma Glucose, Creatinine and calculated Creatinine Clearance (CKD-EPI), Bilirubin Total, Bilirubin Direct and Indirect Albumin, Uric Acid, Urea Nitrogen	At every visit until EOT (inclusive), repeat after EOT only if clinically significant findings at the discretion of investigator.
	Cholesterol, triglycerides	At baseline, weeks 12, 26 and 52.
	hsC-Reactive Protein	At baseline, weeks 12, 26 and 52
	Haptoglobin	At baseline, weeks 12, 26 and 52
Serum Pregnancy test *	Human Serum Chorionic Gonadotropin	At screening and anytime if urinary test is positive.
Urine Pregnancy test *	Human Chorionic Gonadotropin in the urine	At screening, baseline and then every 4 weeks thereafter.
Urinalysis - dipstick	Urine: Nitrite, Protein, Glucose, Ketone, Bilirubin, RBC/ Erythrocytes, WBC/ Leukocytes, pH, creatinine Urobilinogen	At every visit until EOT (inclusive), repeat after EOT only if clinically significant findings at the discretion of investigator.
Urine	Spot protein/creatinine ratio	At every visit for safety/efficacy measurement.

Table 5.2.3:1 Safety and immunology laboratory tests ° (Cont.)

Urine-Sediment (microscopic examination)	Urine: Sediment Bacteria, Cast in Sediment, Squamous Epithelial Cells, Sed. Crys., Unspecified, Sediment RBC/ Erythrocytes, Sediment WBC/ Leucocytes	At every visit or if urine analysis is abnormal according to investigator (reflex test).
Infections screening**	Hepatitis B Surface Antigen (qualitative) Hepatitis B core Antibody Hepatitis C Antibodies (qualitative) HIV-1 and HIV-2 Antibody (qualitative) QuantiFERON-TB Gold***	At screening only for group 2 patients. For group 1 patients only done if suspicion for an infection
Immunoglobulin	IgG, IgM	At baseline, weeks 12, 26 and 52.
Immunology testing	ANA Anti-phospholipid antibodies	At screening for Group 2 only. At baseline for Group 1 only For both groups: week 52.
	Anti-dsDNA,	At screening for Group 2 only. At baseline for Group 1 only For both groups: weeks 12, 26, 52 and EOS.
	Complements C3, C4, anti-C1q antibodies	At baseline for Group 1 and weeks 12, 26, 42(only complements C3 and 4), 52 and EOS.

° Baseline is referring to visit 1 of group 1-patients and visit 2 of group 2 patients. For group 1 patients any lab parameters for visit 1 are already taken during the end of treatment visit of clinical trial 1293-0010 and will not be repeated.

* Urine (dipstick) pregnancy test will be performed prior to study entry and then every 4 weeks in women of child bearing potential. If visit intervals are >4 weeks, dipsticks will be provided to patients to perform the pregnancy test at home. A serum pregnancy test will also be performed at Screening visit. Throughout the trial, if any dipstick test is positive or uncertain, a serum pregnancy test must be collected on the same day for confirmation. Only patients with a negative pregnancy test will be eligible and will continue with trial medication administration.

** Results of infections screening will not be captured in the sponsor's database. In case HB_c positive but HB_s antigen negative then measure Hepatitis B DNA. If result positive, exclude patient; if result negative, patient can be included.

*** In case of an indeterminate result, test should be repeated; in case the result is indeterminate again, a PPD skin test should be performed.

¹ In case HB_c positive but HB_s antigen negative then measure Hepatitis B DNA: if positive exclude patient, if negative patient can be included.

If patient is positive for anti-HCV during the trial, the HCV-RNA test can be performed locally to exclude false positive results. If HCV-RNA test is negative, patient may continue (the result must be documented in eCRF).

All blood samples will be analysed at a designated central laboratory, and if necessary, by additional specialist laboratories, except erythrocyte sedimentation rate (ESR) which will be performed onsite or at a local accredited lab. The central laboratory will provide materials for

all blood sampling including ESR. Instructions for sample collection, handling, processing and shipping are provided in the Laboratory Manual in the ISF.

The central laboratory will send reports to the investigator and will transfer the results of the analysis to the sponsor. It is the responsibility of the investigator to evaluate the laboratory reports. Clinically relevant abnormal findings as judged by the investigator will be reported as adverse events (refer to [Section 5.2.5](#)); and should be repeated using an unscheduled visit lab kit until normalisation or stabilisation or until an alternative explanation has been established.

Mycophenolate blood levels will be collected at all timepoints indicated in the [Flow Charts](#). Samples will be analysed for exploratory purposes after trial completion.

In case the criteria for hepatic injury are fulfilled, a number of additional measures will be performed (please see [Section 5.2.5.1](#) and the DILI Checklist provided in the ISF). The amount of blood taken from the patient concerned will be increased due to this additional sampling.

5.2.4 Electrocardiogram

The 12-lead ECGs will be recorded according to local standard procedures at the visits indicated in the [Flow Charts](#). Automatically generated interval data (PR, QRS, QT) and heart rate on the printed ECG will be collected on the eCRF. QTcB and QTcF will be calculated with HR and QT interval.

Rate, rhythm and repolarisation changes have to be evaluated, compared to previous charts, and assessed for clinical relevance. Clinically relevant abnormal findings will be reported either as baseline conditions (if identified at the screening visit) or otherwise as adverse events and will be followed up and/or treated as medically appropriate. If necessary, additional ECGs may be repeated for quality or safety reasons and the repeated ECG will be used for analysis.

Dated and signed printouts of ECG with findings should be documented in patient's medical record.

5.2.5 Assessment of adverse events

5.2.5.1 Definitions of AEs

Adverse event

An adverse event (AE) is defined as any untoward medical occurrence in a patient or clinical investigation subject administered a medicinal product and which does not necessarily have to have a causal relationship with this treatment.

An AE can therefore be any unfavourable and unintended sign (including an abnormal laboratory finding), symptom, or disease temporally associated with the use of a medicinal product, whether or not considered related to the medicinal product.

Serious adverse event

A serious adverse event (SAE) is defined as any AE which fulfils at least one of the following criteria:

- results in death
- is life-threatening, which refers to an event in which the patient was at risk of death at the time of the event; it does not refer to an event that hypothetically might have caused death if more severe
- requires inpatient hospitalisation or prolongation of existing hospitalisation
- results in persistent or significant disability or incapacity, or
- is a congenital anomaly / birth defect, or
- is deemed serious for any other reason if it is an important medical event when based on appropriate medical judgement which may jeopardise the patient and may require medical or surgical intervention to prevent one of the other outcomes listed in the above definitions.

Examples of such events are intensive treatment in an emergency room or at home for allergic bronchospasm, blood dyscrasias or convulsions that do not result in hospitalisation or development of dependency or abuse.

For Japan only: the following events will be handled as “deemed serious for any other reason”. AEs which possibly lead to disability will be reported as SAEs.

AEs considered “Always Serious”

Cancers of new histology and exacerbations of existing cancer must be classified as a serious event regardless of the duration between discontinuation of the drug and must be reported as described in [Section 5.2.5.2](#), subsections “AE Collection” and “AE reporting to sponsor and timelines”.

In accordance with the EMA initiative on Important Medical Events, Boehringer Ingelheim has set up a list of further AEs, which by their nature, can always be considered to be “serious” even though they may not have met the criteria of an SAE as defined above.

The latest list of “Always Serious AEs” can be found in the electronic data capture (eDC) system. These events should always be reported as SAEs as described above.

Adverse events of special interest (AESIs)

The term AESI relates to any specific AE that has been identified at the project level as being of particular concern for prospective safety monitoring and safety assessment within this trial, e.g. the potential for AEs based on knowledge from other compounds in the same class.

AESIs need to be reported to the sponsor’s Pharmacovigilance Department within the same timeframe that applies to SAEs, please see above.

The following are considered as AESIs:

- Hepatic injury

A hepatic injury is defined by the following alterations of hepatic laboratory parameters:

- an elevation of AST and/or ALT ≥ 3 fold ULN combined with an elevation of total bilirubin ≥ 2 fold ULN measured in the same blood draw sample, and/or
- aminotransferase (ALT, and/or AST) elevations ≥ 10 fold ULN

These lab findings constitute a hepatic injury alert and the patients showing these lab abnormalities need to be followed up according to the “DILI checklist” provided via the eDC system. In case of clinical symptoms of hepatic injury (icterus, unexplained encephalopathy, unexplained coagulopathy, right upper quadrant abdominal pain, etc.) without lab results (ALT, AST, total bilirubin) available, the investigator should make sure these parameters are analysed, if necessary in an unscheduled blood test. Should the results meet the criteria of hepatic injury alert, the procedures described in the DILI checklist should be followed.

➤ Injection reactions including anaphylactic reaction

Any suspicion of severe injection reaction and any potential cases of anaphylaxis should be defined and assessed using the criteria discussed in the statement paper from Sampson HA ([R11-4890](#)).

➤ Cytokine release syndrome

A cytokine release syndrome manifests when a large number of immune cells becomes activated and releases inflammatory cytokines. It is consistently associated with elevated TNF α , IFN γ , and IL-6 levels. The cytokine-release syndrome is clinically characterised by fever, chills, rigor and rash. Other symptoms are nausea, dyspnoea, tachycardia and hypotension. Potentially life-threatening complications of a cytokine release syndrome include cardiac dysfunction, respiratory distress syndrome, neurologic toxicity, renal and/or hepatic failure, and disseminated intravascular coagulation. In case of suspicion of a cytokine release syndrome, it is recommended to measure IL-6 levels in the local laboratory if the assay is available.

In general therapy with BI 655064 is immunosuppressive and potentially could increase the risk for infections or lymphoproliferative diseases.

➤ Opportunistic infections and/or severe infections

Opportunistic infections include pneumocystis pneumonia, toxoplasmosis gondii encephalitis, cryptosporidiosis; microsporidiosis, mycobacterium tuberculosis, mycobacterium avium; bacterial respiratory disease, bacterial enteric infection, mucocutaneous candidiasis, invasive mycoses, CMV, EBV, herpes simplex (invasive only), varicella zoster, human herpesvirus 8, JC virus infection.

Any severe infection should also be reported as AESI.

Whenever a patient comes to a visit and reports of an (S)AE related to infections which occurred in the interval since the last visit, then he/she is routinely asked whether they have been seen/treated by a physician and whether blood samples had been taken in that context. Should this be answered in the affirmative then efforts should be undertaken to collect the respective information.

➤ Lymphoproliferative disorders (e.g. B- and T-cell lymphoma, Non-Hodgkin lymphoma and Hodgkin lymphoma, hepatosplenic T-cell lymphoma)

In case of adenopathy, hepato- or splenomegaly, fever of unclear origin, night sweats or loss of weight, occurrence of lymphoproliferative diseases should be evaluated. As the

occurrence of lymphoproliferative disorders is associated with active EBV-infection, patients suffering from active EBV infection should be carefully evaluated for the occurrence of lymphoproliferative diseases.

➤ **Thrombosis and adjunct immunosuppression**

Immunosuppression may favour a prothrombotic state. Therefore, patients should be carefully followed for early signs of peripheral or central thrombosis or thromboembolic events.

For countermeasures and management of the above mentioned Adverse Events please refer to [section 4.2.2](#) of the protocol.

The specific therapy of the listed AESIs will be according to institutional standards.

Other adverse events

In case during the course of the trial a patient develops a neutropenia with a severity grade higher than 3, it is recommended to first decrease or stop MMF, then to check lab values and decide on the possible root cause of the neutropenia.

Intensity (severity) of AEs

The intensity (severity) of adverse events should be classified and recorded in the eCRF according to the Rheumatology Common Terminology Criteria for Adverse Events (RCTC) Version 2.0 developed by [REDACTED] ([R13-3515](#)). Refer to the ISF for RCTC intensity/severity classification.

Intensity options are:

Grade 1	mild
Grade 2	moderate
Grade 3	severe
Grade 4	life-threatening

Causal relationship of AEs

Medical judgement should be used to determine the relationship, considering all relevant factors, including pattern of reaction, temporal relationship, de-challenge or re-challenge, confounding factors such as concomitant medication, concomitant diseases and relevant history.

Arguments that may suggest that there is a reasonable possibility of a causal relationship could be:

- The event is consistent with the known pharmacology of the drug.
- The event is known to be caused by or attributed to the drug class.
- A plausible time to onset of the event relative to the time of drug exposure.
- Evidence that the event is reproducible when the drug is re-introduced.
- No medically sound alternative aetiologies that could explain the event (e.g. pre-existing or concomitant diseases, or co-medications).
- The event is typically drug-related and infrequent in the general population not exposed to drugs (e.g. Stevens-Johnson syndrome).

- An indication of dose-response (i.e. greater effect size if the dose is increased, smaller effect size if dose is diminished).

Arguments that may suggest that there is no reasonable possibility of a causal relationship could be:

- No plausible time to onset of the event relative to the time of drug exposure is evident (e.g. pre-treatment cases, diagnosis of cancer or chronic disease within days / weeks of drug administration; an allergic reaction weeks after discontinuation of the drug concerned).
- Continuation of the event despite the withdrawal of the medication, taking into account the pharmacological properties of the compound (e.g. after 5 half-lives). Of note, this criterion may not be applicable to events whose time course is prolonged despite removing the original trigger.
- Additional arguments amongst those stated before, like alternative explanation (e.g. situations where other drugs or underlying diseases appear to provide a more likely explanation for the observed event than the drug concerned).
- Disappearance of the event even though the trial drug treatment continues or remains unchanged.

5.2.5.2 Adverse event collection and reporting

AE Collection

The investigator shall maintain and keep detailed records of all AEs in the patient files. The following must be collected and documented on the appropriate eCRF(s) by the investigator:

- From signing the informed consent onwards until the individual patient's end of study:
 - All AEs (serious and non-serious) and all AESIs.
- Patients who discontinue trial medication prematurely and agree to be contacted further, should be followed up as described in [section 3.3.4.1](#). From then on until the individual patient's end of the trial:
 - The investigator must report all deaths/fatal AEs regardless of relationship; related SAEs and related AESIs that the investigator becomes aware of.
- After the individual patient's end of study:
 - The investigator does not need to actively monitor the patient for AEs but should report related SAEs and related AESIs of which the investigator may become aware of by any means of communication, e.g. phone call. Those AEs should, however, not be reported in the eCRF.

[figure not shown]

Figure 5.2.5.2: 1 AE Collection

The REP is defined as 50 days after the last trial drug administration. All AEs that occur during the treatment phase and throughout the REP will be considered as on treatment (see [section 7.3.4](#)). Events that occur after the REP will be considered as post treatment events.

AE reporting to sponsor and timelines

The investigator must report SAEs, AESIs, and non-serious AEs which are relevant for the reported SAE or AESI, on the BI SAE form immediately (within 24 hours) to the sponsor's unique entry point (country specific reporting process will be provided in the ISF). The same timeline applies if follow-up information becomes available. In specific occasions the investigator could inform the sponsor upfront via telephone. This does not replace the requirement to complete and send the BI SAE form.

With receipt of any further information to these events, a follow-up SAE form has to be provided. For follow-up information the same rules and timeline apply as for initial information.

Information required

For each AE, the investigator should provide the information requested on the appropriate eCRF pages and the BI SAE form, if applicable. The investigator should determine the causal relationship to the trial medication and any possible interactions between the trial medication and an Auxiliary Medicinal Product (AMP).

The following should also be recorded as an (S)AE in the CRF and BI SAE form (if applicable):

- Worsening of the underlying disease or of other pre-existing conditions
- Changes in vital signs, ECG, physical examination and laboratory test results, if they are judged clinically relevant by the investigator.

If such abnormalities already pre-exist prior to trial inclusion they will be considered as baseline conditions and should be collected in the eCRF only.

[figure not shown]
All (S)AEs, including those persisting after individual patient's end of study must be followed up until they have resolved, have been assessed as "chronic" or "stable" or no further information can be obtained.

[figure not shown]
[figure not shown]
[figure not shown]
Pregnancy

[figure not shown]
In rare cases, pregnancy might occur in a clinical trial. Once a patient has been enrolled in the clinical trial and has taken trial medication, the investigator must report any drug exposure during pregnancy in a trial participant immediately (within 24 hours) by means of Part A of the Pregnancy Monitoring Form to the sponsor's unique entry point. Similarly, potential drug exposure during pregnancy must be reported if a partner of a male trial participant becomes pregnant. This requires a written consent of the pregnant partner.

The outcome of the pregnancy associated with the drug exposure during pregnancy must be followed up and reported to the sponsor's unique entry point on the Pregnancy Monitoring Form for Clinical Trials (Part B). The ISF will contain the Pregnancy Monitoring Form for Clinical Trials (Parts A and B) as well as information and consent form for the pregnant partner.

As pregnancy itself is not to be reported as an AE, in the absence of an accompanying SAE and/or AESI, only the Pregnancy Monitoring Form for Clinical Trials and not the SAE form is to be completed. If there is an SAE and/or AESI associated with the pregnancy an SAE form must be completed in addition.

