6.2.3.2 Follow-Up (FUp) and End of Study (EOS) Visits

After the EOT visit, patients who have completed the 52-week treatment period will return for a safety FUp visit 4 weeks later, followed by the EOS visit 12 weeks after EOT. In case a patient has to discontinue the trial medication prior to having completed the 52-week treatment period, the patient will be invited to attend a subset of visits as per [section 6.2.3.3](#) below.

The investigator will continue to record and follow-up on all AEs until the residual effect period (REP). Refer to [section 5.2.5.2](#) for AE collection procedures after the REP. At EOS visit, the investigator needs to confirm whether the AEs are sufficiently followed up and provide documentation in the patient's medical records and on the eCRF.

For a detailed description of the trial procedures at FUp and EOS visits, refer to [Flow Charts](#).

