7.3.4 Safety analyses

Adverse events will be coded using the Medical Dictionary for Drug Regulatory Activities (MedDRA). Standard BI summary tables and listings will be produced. All adverse events with an onset between start of treatment and end of the residual effect period (REP), a period of 50 days after the last dose of trial medication, will be assigned to the on-treatment period for evaluation. Analysis will be performed based on randomised treatment.

All treated patients will be included in the safety analysis. In general, safety analyses will be descriptive in nature and based on BI standards. No hypothesis testing is planned. Statistical analysis and reporting of adverse events will concentrate on treatment-emergent adverse events, i.e. all adverse events occurring between start of treatment and end of the REP. Adverse events that start before first drug intake and deteriorate under treatment will also be considered as 'treatment-emergent'.

Frequency, severity and causal relationship of adverse events will be tabulated by system organ class and preferred term after coding according to the current version of the MedDRA at the database lock.

AESIs will be summarized separately using a standard BI summary table. Note that there is one SAE definition specified in [Section 5.2.5.1](#) for Japan only. Laboratory data will be analysed both quantitatively as well as qualitatively. The latter will be done via comparison of laboratory data to their reference ranges. Values outside the reference range as well as values defined as clinically relevant will be summarised. Treatment groups will be compared descriptively with regard to distribution parameters as well as with regard to frequency and percentage of patients with abnormal values or clinically relevant abnormal values.

Vital signs, physical examinations, or other safety-relevant data observed at screening, baseline, during the course of the trial and at the end-of-trial evaluation will be assessed with regard to possible changes compared to findings before start of treatment.

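### The protocol contradicts itself on which adverse events are collected from early stoppers in the 50 days after the last dose, a window the analysis counts as on treatment

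*Protocol*

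**What the plan says.** Protocol section 5.2.5.2 sets the collection rules in bullets.

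- The first bullet applies "From signing the informed consent onwards until the individual patient's end of study" and covers "All AEs (serious and non-serious) and all AESIs". It makes no exception for early stoppers.
- The second bullet opens "Patients who discontinue trial medication prematurely and agree to be contacted further, should be followed up as described in" (the reference is to section 3.3.4.1). After that point, and to the patient's end of trial, its scope is: "The investigator must report all deaths/fatal AEs regardless of relationship; related SAEs and related AESIs that the investigator becomes aware of".
- The same section then states "The REP is defined as 50 days after the last trial drug administration" and "All AEs that occur during the treatment phase and throughout the REP will be considered as on treatment".

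Section 6.2.3.2, whose preceding paragraph covers both completers and early stoppers, says "The investigator will continue to record and follow-up on all AEs until the residual effect period (REP"), and sends the reader to 5.2.5.2 for collection after the REP. Section 6.2.3.3 includes AE collection among the assessments at early stoppers' Week 12, 26, 42 and 52 visits, with no limit by seriousness or causality.

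On the analysis side, protocol 7.3.4 assigns to the on-treatment period "All adverse events with an onset between start of treatment and end of the residual effect period (REP), a period of 50 days", counted from the final injection. SAP 6.1 and 7.8.1 use the same window. SAP 7.8.1 tabulates all AEs, serious AEs, AEs of special interest and maximum toxicity grade by treatment.

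**The concern.** The second bullet of 5.2.5.2 is triggered by stopping the drug, not by the end of the REP. Read literally, it narrows collection at the start of a 50-day window in which the analysis expects all AEs. Three kinds of event would fall out: non-serious AEs, unrelated non-fatal serious AEs, and unrelated non-fatal AEs of special interest. Completers have no such narrowing. Their AEs are collected to the end-of-study visit 12 weeks after end of treatment (EOT), which covers the whole REP. Completeness of the treatment-emergent tables would then depend on completion status, and the SAP has no note to warn the reader.

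The relatedness filter adds a second issue. It depends on investigator judgement, and protocol 3.2 reports that 29 patients were unblinded, 20 of them on treatment. SAP 6.6.1 mentions unblinded placebo patients who were allowed to stop injections. An investigator who knows that a patient received placebo has little reason to call an event drug-related. This is a possible route to capture that differs by arm. The documents do not show that it happened.

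**Working it through.** The plan gives no figure to reproduce on this point. The check compares the passages and then counts days.

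**1. AE scope for an early stopper between last dose and day 50**

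- 5.2.5.2, first bullet: all AEs.
- 5.2.5.2, second bullet: fatal AEs, related serious AEs and related AEs of special interest.
- 6.2.3.2: all AEs, up to the REP.
- 6.2.3.3: AE collection at visits, scope not limited.
- 7.3.4, SAP 6.1 and SAP 7.8.1: all AEs counted to last dose + 50 days.

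The 50 days agree in 5.2.5.2, 7.3.4, SAP 6.1 and SAP 7.8.1. Only the collection scope conflicts.

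**2. Does 6.2.3.2 settle it?** It treats 5.2.5.2 as the rule for the time after the REP, but 5.2.5.2 has no rule that starts when the REP ends. Its triggers are consent, premature discontinuation and end of study. Nor does 6.2.3.2 say whether collection runs to the start or the end of the REP. If the first bullet governed early stoppers throughout, the second would have no effect, so a site could reasonably read the second as an exception.

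**3. Do the visits in 6.2.3.3 settle it?** They show that AEs are asked about, but not which ones. A scheduled visit falls within 50 days of the last dose only for stops at about Weeks 5–11, 19–25, 35–41 or 45–51 (for example, a stop at Week 5 gives 7 × (12 − 5) = 49 days to Week 12). In the section's own example, EOT at Week 26 and next visit at Week 42, the gap is 16 × 7 = 112 days. A later visit can still collect earlier events, so scope is what matters.

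**4. Days affected per early stopper**

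- Restriction from the last dose: 50 days.
- Restriction from the EOT visit, up to 7 days after the last dose (6.2.3.1): at least 50 − 7 = 43 days, or 43/50 = 86% of the REP.

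**5. Share of the AE window.** With t days on drug in this trial, the share is 50/(t + 50). Over the SAP's two-year window, taking 1293.10 as 364 days (assumed), it is 50/(364 + t + 50).

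- Stop at Week 26 (t = 182): 50/232 = 21.6%; two-year 50/596 = 8.4%.
- Stop at Week 12 (t = 84): 50/134 = 37.3%; two-year 50/498 = 10.0%.

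These are shares of calendar time, not of AEs missed.

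**6. Illustration on assumed inputs.** Assume 15 patients per arm (60/4, although SAP 7.4.1 says the groups are unbalanced), 1 to 5 early stoppers per arm, 0.1 to 1.0 first events per patient-year for a given term, and none of these captured. The probability of a missed patient is P = 1 − exp(−rate × days/365.25).

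- Low end, 43 days: P = 1 − exp(−0.1 × 43/365.25) = 0.012; 1 × 0.012 = 0.01 patients, or 0.1 percentage points of 15.
- High end, 43 days: P = 1 − exp(−1.0 × 43/365.25) = 0.111; 5 × 0.111 = 0.56 patients, or 3.7 points.
- High end, 50 days: P = 0.128; 5 × 0.128 = 0.64 patients, or 4.3 points.
- If sites follow 6.2.3.2 and collect all AEs: zero.

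**The case against.** The strongest reply is that the protocol as a whole asks for all AEs. The first bullet of 5.2.5.2 has no exception. The reporting paragraph requires serious AEs and AEs of special interest within 24 hours, whether related or not. Section 6.2.3.2 applies 5.2.5.2 only after the REP. The disputed bullet itself refers to 3.3.4.1, which leads to 6.2.3, where AE collection is unrestricted. Its starting point is loosely worded and could be read as the end of the REP. Figure 5.2.5.2:1 on AE collection, which was not available for this check, may show when the narrower scope begins.

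Most of this stands, and it limits the point to a contradiction. It does not remove it, because the narrow bullet remains in the section that sites use for AE reporting and nothing in the readable text ties it to the end of the REP.

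A reader might go further and infer three things that the documents do not support:

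- *That the protocol asks early stoppers only for fatal and related serious events.* Other passages ask for all AEs, and even the narrow bullet includes related AEs of special interest.
- *That the analysis treats the 50 days as fully observed exposure.* The SAP assigns events to a window and counts patients with AEs. SAP 7.7 ends exposure at the last injection, so no REP person-time enters a denominator.
- *That AEs are in fact under-counted, by about 22%, or in a known direction between arms.* Loss depends on which passage sites followed, and 21.6% is a share of maintenance time for a Week 26 stop. The documents give no discontinuation counts by arm.

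**Conclusion.** The contradiction is real and should be corrected. On the literal reading of one bullet, early stoppers lose part of their AE capture for 43 to 50 days that the analysis counts as on treatment, while completers lose none. On the reading in 6.2.3.2, nothing is lost. The documents do not show which rule sites applied.

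The likely numerical effect on any one term is small: under the assumed rates and arm sizes, from zero to about 0.6 patients per arm. It could be larger for the overall any-AE, serious-AE and special-interest rows, for which the documents give no rates. The direction of any between-arm effect is unknown. Safety analysis is descriptive, so no hypothesis test is at risk. What is at stake is whether the safety tables are equally complete for early stoppers and completers. The conclusion rests on the readable text and would weaken if the AE collection figure places the restriction after the REP.

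**What to change.** Reconcile protocol 5.2.5.2, 6.2.3.2 and 6.2.3.3:

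- In the second bullet of 5.2.5.2, state that all AEs, serious AEs and AEs of special interest are collected from early stoppers to the end of the 50-day REP, and that restricted reporting begins only after that.
- In 6.2.3.2, say that all AEs are recorded to the end of the REP. In 6.2.3.3, state the AE scope at early stoppers' visits before and after it.
- Leave the first bullet's all-AE collection to end of study unchanged for completers. A uniform 50-day limit would shorten it.
- Check that Figure 5.2.5.2:1 agrees.

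For data already collected, the SAP or the trial report should state which rule sites applied. If collection was restricted, it should flag early stoppers' REP data in the listings and footnote the treatment-emergent tables.

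The cost is about one sentence in 5.2.5.2, matching wording in the other two sections, and one statement in the SAP or report. AE collection at early stoppers' visits is already planned.
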